13 DATA QUALITY ASSURANCE

BioMarin personnel or designees will visit the study site prior to initiation of the study to review with the site personnel information about the IP, protocol and other regulatory document requirements, any applicable randomization procedures, source document requirements, eCRFs, monitoring requirements, and procedures for reporting AEs, including SAEs.

At visits during and after the study, a CRA will monitor the site for compliance with regulatory documentation, with a focus on accurate and complete recording of data on eCRFs from source documents, adherence to protocol, randomization (if applicable), SAE reporting and drug accountability records.

Sites will enter study data into eCRFs into the study EDC system. Data Quality Control will be performed by BioMarin Clinical Data Management or designee through implementation of quality control checks specified in the study data management plan and edit check specifications. Additional subject-reported study data may be entered into the study EDC system via electronic diary.

14 STATISTICAL METHODS AND DETERMINATION OF SAMPLE SIZE

14.1 Statistical and Analytical Plans

The statistical analysis plan (SAP) will provide additional details on the planned statistical analysis. Unless otherwise stated, all analyses will be performed using SAS v. 9.4.

14.1.1 Interim Analyses

An interim analysis will be carried out to support NDA/MAA filing. The study team, subjects, and investigators will have no access to the individual subject treatment allocation, and blinded pooled safety outputs will be provided for the randomized subjects.

14.1.2 Procedures for Accounting for Missing, Unused and Spurious Data

Because the completeness of the data affects the integrity and accuracy of the final study analysis, every effort will be made to ensure complete, accurate and timely data collection and, therefore, avoid missing data. In addition, a subject who prematurely discontinues study drug should be asked if they are willing to continue to participate in the study assessments for remaining duration of the study, as long as in the judgment of the investigator such continued participation would not detrimentally affect the health, safety, or welfare of the subject.

No missing data will be imputed for any analysis, except for unless otherwise specified for the efficacy analyses or for the missing dates for AEs and concomitant medications. Missing dates or partially missing dates will be imputed conservatively to ensure that an AE is considered treatment emergent and has the longest possible duration, if the partial information available indicates that the AE is likely treatment emergent.

Additional details regarding the handling of missing data will be provided in the SAP.

14.2 Safety Analysis

The safety analysis will be performed on safety population as defined in Section 14.7.2 and will be considered descriptive.

All AEs will be coded using the most current version of MedDRA will be used by the Sponsor to assign system organ class and preferred term classification to events and diseases, based on the original terms entered on the CRF.

All AEs will be coded using MedDRA. The incidence of AEs will be summarized by system organ class, preferred term, relationship to study treatment (as assessed by investigator), and severity. All AEs, including SAEs and AEs that lead to permanent discontinuation from the study and from the study treatment, will be listed. Hypersensitivity reactions and

symptomatic hypotension are of interest, and the percentage of subjects who report these AEs will be presented. Hypersensitivity reactions will be defined in the SAP.

Clinical laboratory data will be summarized by the type of laboratory test. For each clinical laboratory test, descriptive statistics will be provided on baseline as well as all subsequent visits.

All other safety measures including laboratory tests, vital signs, ECG, echocardiogram, hip clinical assessment, and concomitant medication data will also be summarized descriptively. Data summaries will be presented by treatment group (when applicable) for each cohort and overall. All safety results will be listed.

14.3 Efficacy Analysis

Efficacy analysis will be performed on the efficacy population as defined in Section 14.7.1. Efficacy endpoints include length/height AGV and length/height standard score (Z-score) at Week 52.

For a given interval [Date1, Date2], the AGV is defined as follows:

$$\text{AGV} = \frac{\text{Length/standing height at Day 2} - \text{Length/standing height at Day 1}}{\text{Interval Length (Days)}} \times 365.25$$

where the interval length in days is calculated as Date2 – Date1. AGV will be calculated for the following visits/intervals:

- Baseline: [Date of last length/height measurement in study 901 at least 6 months prior to Day 1 in study 206, Date of Day 1]
- Week 13: [Date of Day 1, Date of Week 13]
- Week 26: [Date of Day 1, Date of Week 26]
- Week 39: [Date of Day 1, Date of Week 39]
- Week 52 (12-month): [Date of Day 1, Date of Week 52]

The baseline of the AGV is established in the natural history study of Study 111-901, based on the standing height measurements in the last 6 months prior to enrollment to Study 111-206. AGV will be summarized using descriptive statistics (mean, SD, median, minimum, and maximum). Results will be summarized by treatment group and cohort.

The measurement of length/standing height will be converted to age-and sex-appropriate standard score (SDS), also referred to as Z-score, by comparison with normal reference standards (not ACH). The Z-score will be summarized similarly to growth velocity.

Comparisons between treatment groups by cohort on these variables will be carried out where appropriate. Statistical comparisons will be considered descriptive. Additional details regarding efficacy analysis will be provided in the SAP.

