9 INVESTIGATIONAL PLAN

9.1 Overall Study Design and Plan

This is a Phase 2 randomized, double-blind, placebo-controlled clinical trial of BMN 111 in infants and younger children with a diagnosis of ACH.

Subjects age \geq 6 months to $<$ 60 months old who have documented ACH confirmed by genetic testing; at least a 6-month period of pretreatment growth assessment in Study 111-901 immediately before study entry; and who meet the study eligibility criteria, will participate. Eligible subjects ranging from 0 months to $<$ 3 months old may enroll directly into 111-206 and have a minimum of 3 months of pretreatment observation prior to commencing treatment with investigational product, or may enroll in 111-901 for a minimum of 3 months of pretreatment growth assessment immediately before roll-over to 111-206.

Approximately 70 subjects will be enrolled at approximately 10-15 clinical centers worldwide.

The primary objectives of this study are to assess the safety and tolerability of daily SC BMN 111 administered to infants and young children with ACH, and evaluate the effect of BMN 111 on Z-scores. Subjects will be enrolled into 3 age cohorts based on age at study screening starting with the eldest population. Within Cohorts 1 and 2, subjects will be stratified by age:

- Cohort 1 – children aged \geq 24 to $<$ 60 months (n \geq 30 total: 3 sentinel subjects who receive BMN 111, and at least 27 additional subjects randomized 1:1 to treatment or placebo control), stratified by age (\geq 24 to $<$ 36 months and \geq 36 months to $<$ 60 months)
- Cohort 2 – children aged \geq 6 to $<$ 24 months (n \geq 20 total: 3 sentinel subjects who receive BMN 111, and at least 17 additional subjects randomized 1:1 to treatment or placebo control), stratified by age (\geq 6 months to $<$ 15 months and \geq 15 months to $<$ 24 months)
- Cohort 3 – children aged 0 to $<$ 6 months (n \geq 20 total: 3 sentinel subjects who receive BMN 111, and at least 17 additional subjects randomized 1:1 to treatment or placebo control). Treatment begins at \geq 3 months to $<$ 6 months after 3 months of observation.

If subjects who enroll in Cohort 3 are not able to begin treatment by $<$ 6 months of age, they will continue in the pretreatment period for another 3 months before enrolling in Cohort 2 to fulfill the pretreatment requirement for Cohort 2.

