The same procedure will be followed for Cohort 3. After all 3 sentinel subjects reach Day 8, the Sponsor will review and evaluate all available safety data and Day 1 PK data. Based on PK data and criteria set in the protocol, the dose may be adjusted for the sentinel subjects and the rest of the cohort, and will be the starting dose for the younger cohort sentinel subjects. Upon review of the clinical and PK data, the remainder of Cohort 3 (≥ 17 additional subjects) will be enrolled and randomized to treatment with BMN 111 or placebo (1:1 ratio).

Cohort 3 subjects must have a minimum of 3 months of observation prior to commencement of treatment. These subjects will have the option to enroll in either 111-901 or 111-206.

Additional sentinels may be added to any cohort if needed for additional safety and/or PK assessment.

As subjects age on study, they will be administered the dose determined to be appropriate for their current age. For example, if a subject enrolls into Cohort 2 at age 20 months, they will receive the recommended dose for subjects aged ≥ 6 to < 24 months until they turn 24 months in age. When they turn 24 months in age, they will begin to receive the recommended dose for subjects aged ≥ 24 to < 60 months.

Each treated subject will have expanded outpatient safety monitoring for a minimum of 3 days of dosing, during which they will be closely observed and non-invasive hemodynamic monitoring will be conducted for at least 4-8 hours post-dosing. Because younger children may not be able to verbalize complaints of dizziness or lightheadedness that are potentially associated with hypotension, study personnel and caregivers will be trained to recognize the signs of hypotension in this population, which may include tachycardia, pallor, diaphoresis, lethargy, delayed capillary refill, and poor feeding. Appropriate rigorous training will be required for parents and caregivers prior to daily injections at home. Training includes the storage, reconstitution, and administration of BMN 111, as well as documentation/reporting of AEs and vigilance for signs of hypotension.

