9.3.1 Inclusion Criteria

Individuals eligible to participate in this study must meet all of the following criteria:

1. Diagnosis of ACH, confirmed by genetic testing. If subjects had previous genetic testing, subjects must have a lab report from a certified laboratory with the study specific mutation documented.
2. Age 0 to < 60 months, at study entry (Day 1)
3. Cohort 1 and 2 subjects must have at least a 6-month period of pretreatment growth assessment in Study 111-901 immediately before screening, and have one documented measurement of height/body length a minimum of 6 months prior to the screening visit for 111-206. Cohort 3 subjects must have a minimum of 3 months of observation prior to treatment. This observational period can be obtained either (1) via prior enrollment in Study 111-901 or (2) via enrollment in this Study 111-206 for a minimum of 3 months of non-treatment observation prior to commencement of treatment.

4. Parent(s) or guardian(s) (and the subjects themselves, if required by local regulations or ethics committee) are willing and able to provide written, signed informed consent after the nature of the study has been explained and prior to performance of any research-related procedure
5. Willing and able to perform all study procedures as physically possible
6. Parent(s) or caregiver(s) are willing to administer daily injections to the subjects and complete the required training

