9.4.6 Selection of Dose and Dosing Schedule Used in the Study

Study 111-202, the second clinical trial in humans and the first in children with ACH, is an ongoing Phase 2, open-label, sequential-cohort, dose-escalation study that assesses daily SC BMN 111 in pediatric subjects with ACH aged 5-14 years with doses ranging from 2.5 µg/kg to 30 µg/kg.

Analysis of safety data from the 6-month initial phase of Study 111-202 showed that treatment with BMN 111 for 6 months at the doses of 2.5, 7.5, 15, and 30 µg/kg was generally well tolerated. The most common AEs across all cohorts were injection site reactions, asymptomatic hypotension, headache, and nasopharyngitis. Based on previous experience of the ongoing Phase 2 clinical trial, including the 24-month data cut at 15 µg/kg, injection site reactions have been identified as risks associated with BMN 111 injections. For a detailed summary of risks, please refer to the current version of the Investigator's Brochure supplied by BioMarin.

Analysis of efficacy data from the 6-month initial phase of Study 111-202 showed that subjects treated with BMN 111 for 6 months at doses ranging from 2.5 to 15 µg/kg daily had a dose-dependent improvement in AGV, with ~50% improvement in AGV seen at the 15 µg/kg dose. The data from Cohort 4 (30 µg/kg) show an apparent greater than dose-proportional increase in BMN 111 plasma exposure (C_{max} and AUC_{0-t}), with a marginal improvement in both absolute AGV and change from baseline AGV after 6 months of BMN 111 treatment when compared with Cohort 3 (15 µg/kg).

Efficacy/toxicity studies have been conducted in neonatal and very young animals (7-day postpartum mouse and rat) in both a disease (TD mouse) and non-disease (rat) model. Given that this is the first study in infants and young children, an age-based cohort study design is used to assess safety and PK in young children (Cohort 1, ≥ 24 to < 60 months) prior to dosing toddlers (Cohort 2, ≥ 6 to < 24 months) and infants (Cohort 3, 0 to < 6 months). PK will be monitored and evaluated; Day 1 PK data from the sentinel subjects will inform dose selection modification for the sentinel subjects and for the rest of the cohort to target the observed exposure of the 15-µg/kg dose group in Study 111-202.

Safety, efficacy and PK data from Study 111-202, a Phase 2 study in children with ACH, where a dose of 15 µg/kg has been and continues to be studied, are expected to be the most relevant, and translatable to this study (111-206).

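### The single baseline AGV interval in Section 14.3 cannot be applied to Cohort 3, so change from baseline in AGV is undefined for that cohort as written

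*Protocol*

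**What the plan says.** Section 14.3 of the protocol (Amendment 2) lists the AGV intervals. The baseline entry reads "Baseline: [Date of last length/height measurement in study 901 at least 6 months prior to Day 1 in study 206, Date of Day 1", and no exception is made for any cohort. The same section then describes the Study 111-901 baseline as "based on the standing height measurements in the last 6 months prior to enrollment to Study 111-206".

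The eligibility and design sections set a different requirement for the youngest infants. Section 9.3.1, criterion 3, states "Cohort 3 subjects must have a minimum of 3 months of observation prior to treatment" and allows this to be met "via enrollment in this Study 111-206 for a minimum of 3 months of non-treatment observation". Section 9.1 adds "These subjects will have the option to enroll in either 111-901 or 111-206". Section 7.3.1 gives the same split for baseline growth data: at least 6 months for Cohorts 1 and 2, and at least 3 months for Cohort 3.

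Section 9.1 has Cohort 3 start treatment at 3 to <6 months of age. Infants who cannot start in time do not stay in Cohort 3: "they will continue in the pretreatment period for another 3 months before enrolling in Cohort 2 to fulfill the pretreatment requirement for Cohort 2".

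Section 8 makes the effect on change from baseline in AGV a secondary objective for the whole study population. The synopsis has AGV and its change from baseline summarised by treatment group and cohort, with 95% confidence intervals and p values for treatment comparisons, all regarded as descriptive.

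**The concern.** The baseline rule in Section 14.3 suits children who come through six months of Study 111-901. It was not adapted to the 3-month observation design that the same protocol sets for Cohort 3. Two conditions fail separately. The interval is longer than a treated Cohort 3 infant has been alive, and the named source study may hold no data for that infant. Shortening the interval alone would therefore not make the rule work.

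At stake is the change-from-baseline form of AGV in the youngest cohort. An analyst who follows the protocol has no value to report there. One who reports a value must first choose a window and a data source that the protocol does not give. With no rule fixed, that choice could be made after data have accrued.

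**Working it through.** **Planned numbers.** Section 9.1 gives 3 sentinels plus at least 27 randomised in Cohort 1, and 3 plus at least 17 in each of Cohorts 2 and 3.

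- Enrolled: (3+27) + (3+17) + (3+17) = 70, which reproduces the stated approximate total.
- Randomised: 27 + 17 + 17 = 61.

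**Can any treated Cohort 3 infant satisfy the rule?** Age at the latest admissible baseline measurement = age at Day 1 − 6 months. With the 3-month observation that the protocol requires of Cohort 3, it is age at Day 1 − 3 months.

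| Age at Day 1 (months) | Under the 6-month rule | Under a 3-month rule |
|---|---|---|
| 3 | −3 | 0 |
| 4 | −2 | 1 |
| 5 | −1 | 2 |
| 5.99 | −0.01 | 2.99 |

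Every entry in the middle column falls before birth, so no infant qualifies. Cohort is assigned by age at screening, which can precede Day 1 by up to 30 days. That opens no gap, because an infant who reaches 6 months untreated is moved to Cohort 2. Under a 3-month rule every entry is at or after birth.

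**Which Day 1?** Table 9.1.2 labels the start of the 111-206 observation period Day 1 (Month 0), so a directly enrolled infant has two visits called Day 1. Taking the observation Day 1 does not help. Section 9.3.3 puts that entry at no more than 3 months of age, so six months earlier lies even further before birth.

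**Does the second sentence rescue the rule?** It looks within the last 6 months, where the bullet looks at least 6 months back. It could supply a start point for a Cohort 3 infant observed in Study 111-901. It still relies on 111-901, so it supplies none for an infant observed only in 111-206.

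**Share affected.**

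- Randomised: 17/61 = 27.9%.
- Enrolled, with sentinels: 20/70 = 28.6%.
- These are planned minimums. With 17 in Cohort 3, the share stays above a quarter up to 67 randomised (17/67 = 25.4%) and equals 25% at 68.

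**What is not affected.** AGV at Weeks 13, 26, 39 and 52 runs from Day 1 and uses no pretreatment interval. Change in length/height Z-score, the primary efficacy endpoint (Section 9.12.2), needs only a baseline length and follow-up lengths.

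**The case against.** The strongest reply is that the intended baseline is clear. Sections 7.3.1 and 9.3.1 both give 6 months for the older cohorts and 3 for the youngest, so Section 14.3 merely failed to carry this over, and it leaves further efficacy detail to the SAP, which was not available for this review. The endpoint is secondary, comparisons are descriptive, and there was no formal sample size calculation. All of that stands and limits the weight of the point. It does not remove it. The protocol states a specific rule that fails against its own design, so an SAP that repeats the rule loses the cohort and one that departs from it contradicts the protocol. Nor does Section 7.3.1 define the interval for infants observed within 111-206.

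Three stronger readings are tempting and are not supported:

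- A reader might infer that the youngest cohort drops out of the AGV analysis. It does not. Post-baseline AGV can be computed in both arms and compared between them; only change from baseline is lost.
- A reader might infer that infants who age out of the 111-206 observation period into Cohort 2 have no Study 111-901 data. Section 9.1 does not say in which study the extra 3 months are spent, and Table 9.1.2 shows no visit after 3 months. The text is unclear on this; it does not establish a gap.
- A reader might take standing height to mean that infants must stand. The AGV formula in the same section uses length or standing height, so this is loose wording.

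**Conclusion.** The point holds in limited form. Taken literally, the baseline AGV rule can be met by no treated Cohort 3 infant, which leaves change from baseline in AGV undefined for at least 17 of 61 randomised subjects (27.9%). The only assumptions are the protocol's own age limits and its planned minimum cohort sizes. The second sentence in Section 14.3 contradicts the first on the window and does not repair it.

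The consequence is confined to one secondary, descriptive endpoint in one cohort. It is not a threat to the primary efficacy endpoint, nor to AGV measured from Day 1. It should still be corrected before analysis, because the contradiction lies in the protocol's own text and the correction costs almost nothing.

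**What to change.** In Section 14.3, define the baseline AGV interval by cohort, in line with Sections 7.3.1 and 9.3.1:

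- Cohorts 1 and 2: keep a start point at least 6 months before Day 1.
- Cohort 3: run from the earliest length in Study 111-901 or in the 111-206 observation period, about 3 months or more before the first dose, to the first-dose Day 1.
- State that Day 1 means the day of first dose, not Day 1 (Month 0) of Table 9.1.2.
- Replace standing height with length/height, and reconcile the two 6-month phrases so that only one window is stated.
- In Sections 9.1 and 9.3.1, state which study supplies the pretreatment data for Cohort 3 infants who move to Cohort 2, and let the baseline rule admit that source.

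The cost is wording in the protocol, and in the SAP if it repeats the rule. For infants observed within 111-206, Table 9.1.2 already schedules anthropometry at Month 0 and at 3 months. For those observed in 111-901, Section 7.3.1 says at least 3 months of growth data are collected. No new procedure is needed.

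The one downside is precision. Annualizing a 3-month change multiplies it, error included, by about 12/3 = 4, against 12/6 = 2 for a 6-month change, so the Cohort 3 baseline will be noisier. The protocol gives no measurement SD from which to size this.

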8 STUDY OBJECTIVES

The primary objectives of the study are to:

- Evaluate the safety and tolerability of BMN 111 in children age 0 to < 60 months with ACH
- Evaluate the effect of BMN 111 on change from baseline in length/height Z-score

The secondary objectives of the study are to:

- Evaluate the effect of BMN 111 on change from baseline in AGV throughout the 52 weeks of the study
- Evaluate the effect of BMN 111 on bone morphology/quality by X-ray and dual X-ray absorptiometry (DXA)
- Evaluate the PK of BMN 111 in children age 0 to < 60 months with ACH
- Evaluate hip function
- Evaluate for hip, thigh, or knee pain, or change in gait
- Evaluate the effect of BMN 111 on HRQoL, developmental status, and /functional independence using age-specific QoL and functional independence questionnaires/QOL status (Bayley Scales of Infant and Toddler Development, Third edition [Bayley-III], Activity of Daily Living and Functional Independence Measure (Wee-FIM), Infant Toddler Quality of Life Questionnaire (ITQOL), Child Behavior Checklist (CBCL))
- Evaluate immunogenicity of BMN 111 and assess impact on safety, PK, and efficacy measures
- Evaluate the effect of BMN 111 on bone metabolism and BMN 111 pharmacodynamic biomarkers
- Evaluate the effect of BMN 111 on growth parameters and body proportions, including change from baseline in upper:lower body segment ratio
- Evaluate the effect of BMN 111 on sleep apnea
- Evaluate the effect of BMN 111 on skull and brain morphology, including foramen magnum, ventricular and brain parenchymal dimensions
- Describe the incidence of surgical interventions, including cervical decompression, adenotonsillectomy, and tympanostomy

The exploratory objectives of the study are to:

- Document physical and phenotypic changes with clinical photography (optional)
- Evaluate genomic biomarkers (optional)

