9.12.2 Primary Efficacy Variables

The primary efficacy endpoint is change from baseline in length/height Z-score.

Growth measures may be collected approximately the same time each visit (\pm 2 hr from the time when the first measurement assessment was taken at Screening) by a study staff member, preferably the same person throughout the study, who has been trained by a BioMarin representative. Standardized measuring equipment and detailed measurement techniques are detailed in the Anthropometric Measurement Guidelines.

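### Efficacy is specified cohort by cohort, and the protocol names no trial-level estimate of its primary endpoint

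*Protocol*

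**What the plan says.** Section 8 states the primary efficacy objective once, with no split by cohort: "Evaluate the effect of BMN 111 on change from baseline in length/height Z-score". Section 9.12.2 matches it: "The primary efficacy endpoint is change from baseline in length/height Z-score". The study population is children aged 0 to <60 months.

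Section 9.1 sets minimum randomised numbers of 27 in Cohort 1 and 17 each in Cohorts 2 and 3, allocated 1:1. It adds: "Within Cohorts 1 and 2, subjects will be stratified by age". Three sentinel subjects per cohort receive BMN 111 without randomisation. They fall outside the efficacy population of Section 14.7.1, and the synopsis summarises them separately.

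For efficacy, Section 14.3 says of growth velocity (AGV) "Results will be summarized by treatment group and cohort", asks for the Z-score to be summarised in a similar way, and then says "Comparisons between treatment groups by cohort on these variables will be carried out where appropriate". The synopsis repeats the by-cohort comparison and promises 95% intervals and p values. Section 14.3 also says "Statistical comparisons will be considered descriptive" and "Additional details regarding efficacy analysis will be provided in the SAP".

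For safety, Section 14.2 reads differently: "Data summaries will be presented by treatment group (when applicable) for each cohort and overall". Section 14.6 reports that no formal sample size calculation was made.

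**The concern.** The primary efficacy question is about one population, but the only comparison the protocol specifies is made separately in up to three age cohorts. The overall level is written for safety and is absent from efficacy in both places where the efficacy analysis is described.

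Two of the three comparisons would rest on 8 or 9 children per arm. If the analysis is run as written, the reader gets up to three wide intervals, each with its own p value, and no single estimate that answers the primary objective. The precision available from 61 randomised children would go largely unused. Descriptive estimates also need intervals narrow enough to be informative.

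**Working it through.** **Plan's own figure.** The total of about 70 has no alpha, power, effect or SD behind it, so no sample size formula can be reproduced. The cohort minima do add up to it: 30 + 20 + 20 = 70, which is 9 sentinels plus 27 + 17 + 17 = 61 randomised.

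**Inputs.** From Section 9.1, with 1:1 allocation: about 13 v 14 in Cohort 1, and 8 v 9 in each of Cohorts 2 and 3. The 95% level comes from the synopsis. A common SD across cohorts is assumed.

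**Within a cohort.** Half-width = t(0.975, n1+n2−2) × SD × √(1/n1 + 1/n2).
- Cohort 1: 2.060 × √(1/13 + 1/14) = 2.060 × 0.385 = 0.79 SD
- Cohort 2 or 3: 2.131 × √(1/8 + 1/9) = 2.131 × 0.486 = 1.04 SD

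**Cohort-stratified over all 61.** Each cohort's weight is n1·n2/(n1+n2).
- Weights: 13×14/27 = 6.741, then 8×9/17 = 4.235 twice; the sum is 15.211
- SE = SD/√15.211 = 0.256 SD
- Half-width with 61 − 4 = 57 df: 2.002 × 0.256 = 0.51 SD

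The stratified interval is about half as wide as that of Cohort 2 or 3 (0.51/1.04 = 0.49) and about two thirds as wide as that of Cohort 1 (0.51/0.79 = 0.65). No gain from adjusting for baseline Z-score is counted.

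**Primary endpoint, Z-score.** The protocol gives no SD for the Z-score change. Half-widths over a range of assumed SDs:

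| Assumed SD | Cohort 2 or 3 | Cohort 1 | Stratified, all 61 |
|---|---|---|---|
| 0.3 | 0.31 | 0.24 | 0.15 |
| 0.5 | 0.52 | 0.40 | 0.26 |
| 0.7 | 0.73 | 0.56 | 0.36 |
| 1.0 | 1.04 | 0.79 | 0.51 |

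**Illustration only, AGV.** Section 7.3.2 gives a 6-month change of 2.01 (SD 1.999) cm/yr at 15 µg/kg in Study 111-202, which was open-label and in older children. AGV is a secondary endpoint here.

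| SD (cm/yr) | Cohort 2 or 3 | Cohort 1 | Stratified, all 61 |
|---|---|---|---|
| 1.5 | 1.55 | 1.19 | 0.77 |
| 1.999 | 2.07 | 1.59 | 1.03 |
| 2.5 | 2.59 | 1.98 | 1.28 |

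At SD 1.999, a difference of 2.01 observed in Cohort 2 or 3 would have a lower limit of 2.01 − 2.07 = −0.06. In Cohort 1 it would be 2.01 − 1.59 = 0.42, and in the stratified analysis 2.01 − 1.03 = 0.98.

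**The case against.** The strongest reply is that efficacy details are left to the SAP, which is not shown, and that comparing by cohort does not forbid a pooled analysis. That stands in part. A reader might infer that the trial will produce no overall estimate, or that the protocol has decided to ignore the randomisation strata and the baseline Z-score. The text supports neither reading: it states no efficacy model, and silence on covariates is not a decision. But the level of comparison is not left silent. It is stated as by cohort in two places, and the SAP is to supply further detail on that, not a different level.

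Second, this is a Phase 2 study with descriptive comparisons and cohort sizes given as minima, so no promise of power is broken. That stands.

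Third, a reader might infer that all three cohort comparisons must be inconclusive, or that the intervals for the primary endpoint are as wide as the expected effect. Neither is supported. At the Study 111-202 figures the Cohort 1 half-width is 1.59/2.01 = 79% of the effect, so the interval there would exclude zero. The 2.01 figure is an uncontrolled change in a different endpoint, and the protocol does not present it as the effect expected here.

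Fourth, the cohorts may not be fully alike. Under Section 9.1.1 the dose may be adjusted only if the sentinels' mean exposure falls outside the 25th to 75th percentile of the reference group, and limits apply, so equal exposure across cohorts is an aim and not a given. By-cohort reporting also suits a first study in infants. These are good reasons to keep the cohort results, but not to leave out an overall one: allocation is 1:1 within each cohort, so a stratified difference is not confounded by age, and the Z-score is already standardised for age and sex.

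**Conclusion.** The point holds as a weakness of precision and estimand. As written, the protocol specifies by-cohort efficacy comparisons and names no trial-level estimate for a primary objective that covers one population. A cohort-stratified estimate would have a half-width of about 0.51 SD, against 1.04 SD in Cohort 2 or 3 and 0.79 SD in Cohort 1.

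These figures rest on the minimum cohort sizes, near-equal arms, complete data and a common SD. If the SD is larger in infants only, the Cohort 1 figure does not change, the Cohort 3 interval widens, and the overall interval changes less than the Cohort 3 one; the figures do not all scale together. The AGV figures in cm/yr illustrate scale and say nothing direct about the Z-score.

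The documents do not support going further and calling the trial underpowered or saying that pooling is excluded.

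**What to change.** Add one sentence to Section 14.3 and to the synopsis. It should name an overall BMN 111 minus placebo difference in Week 52 change in length/height Z-score, with its 95% confidence interval, over all randomised subjects who received a dose. The estimate should be adjusted for the randomisation age strata (or cohort) and for baseline Z-score. Keep the cohort-specific estimates and intervals beside it.

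Sex, the separate randomisation within cohorts in Japan (Section 9.4.5) and any other covariates can be settled in the SAP. If AGV is also analysed overall, state that the Cohort 3 baseline may rest on 3 months of observation where Cohorts 1 and 2 require 6 (Section 9.3.1).

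The cost is one further model per endpoint, with no extra subjects, visits or data. The drawback is that, if the effect differs by age, the overall figure is an average over cohorts, which is why the cohort results should stay next to it.
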